6.6. Guidance for Vivatmo *pro*TM Testing Procedure

Fractional exhaled nitric oxide (FeNO) measurements should be performed according to the American Thoracic Society (ATS) and European Respiratory Society (ERS) Guidelines. Study subjects should be tested while in the seated position, preferably using a chair with arms and without wheels, and without using a nose clip. Subjects should maintain good posture with head slightly elevated. Vivatmo *pro*TM measurements should be made prior to spirometry measurements. When possible perform serial Vivatmo *pro*TM measurements at the same time of the day.

Subjects should inhale to total lung capacity and then exhale into the mouthpiece of the Vivatmo *pro*TM handheld unit at a constant pressure and stable flow rate for 10 seconds guided by visual cues and auditory cues on the display of the Vivatmo *pro*TM base station. Results are processed using dedicated software and in approximately 5 seconds, the NO concentration is displayed on the device in parts per billion (ppb).

The exhalation may be repeated after a brief rest period until 2 acceptable measurements are obtained. A total of up to 10 exhalations may be performed in order to achieve 2 acceptable measurements. The Vivatmo *pro*TM mouthpiece should be changed after every 5 exhalation attempts and recorded appropriately on Study Case Report Form (CRF).

The Vivatmo *pro*TM measurements, spirometry measurements, and asthma control questionnaire information collection may be performed in any sequence at a given patient visit so long as they are all performed on the same day.

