Study Endpoints	
Primary Endpoint: The primary analysis variable will be the percent change of the fractional exhaled nitric oxide (FeNO) measurement made at Visit #1 compared to Visit #2 using the Vivatmo pro™. The first valid FeNO measurement made at each visit will be used for this comparison analysis.
 
Secondary Outcome Measures:
 
 • The change in standard outcome measures (asthma symptoms and spirometry) between Visit #1 to Visit #2 • Repeatability as assessed by replicate FeNO measurements (N=2) at one or more visits. The first two valid FeNO measurements made for each subject at each visit will be used for this repeatability analysis. • Success rate (proportion of patients with successful measurement)
Subject Inclusion / Exclusion Criteria	
See criteria starting on page 23.

Study Procedures	
 Patients meeting study inclusion/exclusion criteria will be consented and will be enrolled in the study. Subjects will be observed during each of two study visits according to routine clinical diagnosis and treatment standards for uncontrolled asthma patients and will have asthma symptoms recorded using a standardized Asthma Control Questionnaire (ACQ). Subjects will have fractional exhaled nitric oxide (FeNO) and spirometry measured and documented at each visit. All study subjects will be asked to perform two valid fractional exhaled nitric oxide (FeNO) measurements at each study visit using the Vivatmo proTM with a limit of 10 total exhalation attempts per subject per visit. If only one valid measurement is taken, it will be used for comparative analysis. No repeatability data will be available for this subject. One operator will guide each subject through the fractional exhaled nitric oxide (FeNO) measurements at each visit. At the first visit, after all study assessments (FeNO, Spirometry, ACQ), subjects will receive therapy by prescription of inhaled corticosteroid (ICS) medication according to routine treatment standards. Subjects will return after 2 weeks (14 days) of treatment for a repeat of measurements.

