3.3. Number of Subjects

The study is designed to enroll patients that have clinically diagnosed signs and symptoms of uncontrolled asthma and who are candidates for inhaled corticosteroid (ICS) treatment. The study will enroll 120 male and female asthma subjects from 7 to 80 years of age. This will include a target of 40 pediatric subjects (approximately 30% of enrollment) from 7 to 17 years of age and a target of 80 adult subjects (approximately 70% of enrollment) from 18 to 80 years of age. This is estimated to be a sample size sufficient to demonstrate device performance in the intended use population of pediatric and adult patients.. The Sponsor may extend the overall enrollment goal and/or suspend enrollment of adult subjects in order to reach a minimum required number of enrolled pediatric subjects.

It is the goal of the study to include moderate to severe asthma patients to the maximum extent possible and as per the professional discretion of participating physician investigators.

Enrollment should optimally include newly diagnosed asthma patients, but may also include those patients with a previous history or diagnosis of uncontrolled asthma who have not been using corticosteroids for at least 4 weeks prior to study Visit #1. Patients currently using a short-acting inhaled bronchodilator medication (also known as a “rescue inhaler”) or leukotriene modifiers may be enrolled, but should not participate if they have used these medications within one hour of either study Visit #1 or study Visit #2 Vivatmo *pro*TM readings. Patients using inhaled corticosteroids, oral corticosteroids, or who are taking biologic immunotherapy medications should not be enrolled.

Measured FeNO levels from the subject population are expected to encompass the full Vivatmo *pro*TM measurement range from 5 ppb to 300 ppb. If a maximum range measurement goal of 270 ppb is not met by enrollment of 120 subjects then additional subjects may be enrolled until the maximum range measurement goal is met.

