3.5. Duration of Study Subject Participation

Study subject participation will take approximately 50 minutes for visit #1 and 30 minutes for visit #2. At the first study visit subjects will be screened, consented, enrolled, assigned a Study Subject ID number (~10 minutes). Subjects will then be instructed on use of the Vivatmo *pro*TM (~10 minutes) and then undergo Vivatmo *pro*TM measurement (~10 mins), spirometry (~10 mins), and ACQ assessment and Case Report Form (CRF) questions (~10 mins). Vivatmo *pro*TM measurement, spirometry, ACQ assessment, and CRF questions will be repeated at the second study visit. At each study visit subjects will be asked to attempt up to 10 exhalation breaths to achieve 2 valid Vivatmo *pro*TM measurements (excluding exhalations for spirometry). Study timing does not include patient counseling for ICS prescription and recommended usage.

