4. STUDY POPULATION

4.1. Asthma Patients who are Candidates for Study Enrollment and Inhaled Corticosteroid (ICS) Treatment

Potential study subjects may be recruited from those already scheduled for clinic visits. Subjects qualified for study participation should (1) have a confirmatory diagnosis of uncontrolled asthma made by a physician and (2) have not used inhaled corticosteroids or oral corticosteroids within 4 weeks prior to enrollment. Use of a short-acting inhaled bronchodilator, leukotriene modifier, or any rescue inhaler will be permitted before the study, but not within one hour of either Vivatmo *pro*TM study reading. Subjects may be prescribed or use a rescue inhaler if necessary during the study and between study Visit #1 and study Visit #2.

Eligible study subjects should be diagnosed with uncontrolled asthma and some degree of presumed lung inflammation. According to guidelines a diagnosis of uncontrolled asthma is established by determining that:

- Symptoms of recurrent airway obstruction are present, based on patient history and examination.
- Patient has symptoms of cough, recurrent wheezing, recurrent difficulty breathing, or recurrent chest tightness are present.
- Symptoms occur or worsen at night or with exercise, viral infection, exposure to allergens and irritants, changes in weather, hard laughing or crying, stress, or other factors.

Long term asthma management is assessed and monitored by:

- Assessing at each visit asthma control, proper medication usage, written asthma action plan, patient adherence, and patient concerns.
- Obtaining lung function measurements by spirometry at least every 1–2 years; more frequently for asthma that is not well controlled.
- Determining if therapy should be adjusted, maintained, stepped-up if needed, stepped-down, if possible.

To these general diagnostic procedures Vivatmo *pro*TM FeNO measurement will be added after taking full account of the uncontrolled asthma diagnosis and guidelines described above. Vivatmo *pro*TM FeNO results will not be used for diagnostic decisions or to confirm the presence of asthma.

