6.4. Patient Screening and Consent

Subjects will optimally be selected from those already scheduled for clinic visits. Prior to study participation and the collection of any study data the PI, and designated study coordinator, will obtain informed consent from each subject who meets inclusion/exclusion criteria. The date of informed consent and confirmation of compliance with study inclusion/exclusion criteria will be recorded on the designated study CRF. Upon completion of consent subjects will be enrolled into the study and this will optimally occur after confirmation of a clinical diagnosis of asthma and prior to prescription of inhaled corticosteroid (ICS) treatment. Diagnosis of asthma may require spirometry measurement.

6.5. Guidance for Preparing and Training Study Subjects on Use of the Vivatmo *pro*TM

Study Coordinators, designated testers, and study subjects should wash their hands prior to using the Vivatmo *pro*TM device for testing. The study coordinator should explain the test to the subject and demonstrate appropriate techniques. It is recommended that study coordinators train subjects (especially children) on proper grasping technique and exhalation technique prior to performing the first Vivatmo *pro*TM measurement. Training may involve practice with holding and positioning the handheld component and practicing a controlled exhalation using a “Flow Be” floating ball toy (where constant exhalation flow/rate causes a toy ball to be suspended in air), using a musical instrument, or other equivalent simulation. The test assumes a full inhalation before beginning.

The subject may need to be prompted or encouraged to “blow” the air from their lungs. Enthusiastic coaching of the subject using appropriate body language and phrases, such as “keep going”, may be required. Encouragement, detailed but simple instructions, lack of intimidation, and visual feedback from the instrument are important in helping children to perform the test.

It is helpful to observe the subject to check for distress and to observe the Vivatmo *pro*TM base station display during the test to help ensure correct effort. If the patient feels “dizzy” testing should be stopped. Well-fitting false teeth should not be routinely removed, since they preserve oropharyngeal geometry and results may generally be better with them in place. Correct patient performance (exhalation flow rate) is required for the measurement to be considered valid.

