6.9. Guidance for ACQ Data Collection

Subject responses to questions on the standardized Asthma Control Questionnaire (ACQ) will be obtained at any time during the study visit. This information will frequently be available prior to Vivatmo *pro*TM testing at the time of confirmation of a clinical diagnosis of asthma. ACQ responses will be recorded at each of the 2 study visits. ACQ responses will be recorded in the designated study case report form (CRF).

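### Section 6.6 asks for FeNO before spirometry, then allows any order on the day, and nothing elsewhere fixes the order or asks for the same order at both visits (minor)

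*Combined protocol and SAP*

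**What the plan says.** Two sentences in section 6.6 (Guidance for Vivatmo pro Testing Procedure) govern test order. The first paragraph states that device "measurements should be made prior to spirometry measurements". The last paragraph names FeNO, spirometry and the ACQ together and says they "may be performed in any sequence at a given patient visit so long as they are all performed on the same day". The only condition attached is the calendar day.

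For the ACQ, section 6.9 already gives full freedom: responses "will be obtained at any time during the study visit".

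The synopsis (Study Procedures) and sections 3.1, 3.5, 6.2 and 6.3 name FeNO before spirometry when they describe the visits. Section 3.5 comes closest to a sequence. It walks through Visit 1 as instruction, FeNO, spirometry, then ACQ and case report form questions, with a time estimate for each. For Visit 2 it says only that device "measurement, spirometry, ACQ assessment, and CRF questions will be repeated at the second study visit".

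The primary endpoint (synopsis and section 3.2) is the percent change in FeNO between the visits, using the first valid measurement at each. The synopsis describes a non-randomized, single cohort study.

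**The concern.** The two sentences in section 6.6 give sites incompatible instructions about the measurement on which the primary endpoint rests. If the first is read as a preference and the second as a permission, they can coexist, but then FeNO-first binds nobody.

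The order matters only through the comparison between visits. In a controlled trial, a procedural difference between visits would be expected to affect both arms and largely cancel. Here there is no second arm, so a systematic difference in how FeNO is taken at Visit 1 and Visit 2 would be counted as part of the change after inhaled corticosteroid treatment. At stake is a component of the primary estimate that could not be separated from the treatment response afterwards, especially if test order is not recorded.

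**Working it through.** The plan gives no figure for an order effect, so there is nothing to reproduce. The check is textual, followed by one line of algebra.

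**1. Does any other section settle the order?**

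| Place | What it contributes | Binding on FeNO versus spirometry? |
|---|---|---|
| 6.6, first paragraph | FeNO should come first | Undone by the last paragraph |
| 6.6, last paragraph | Any order, same day | Explicit permission |
| Synopsis, Study Procedures | Bracketed list; fixes only that the assessments precede the prescription | No |
| 3.1, 6.2, 6.3 | Lists of visit contents | No |
| 3.5 | Time estimates for Visit 1; tests repeated at Visit 2 | No |
| 6.9 | ACQ at any time in the visit | Not about this pair |

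No section resolves the conflict. Because section 6.9 already frees the ACQ, the one practical effect left for the last paragraph of section 6.6 is to free the order of FeNO and spirometry.

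**2. Does any section ask for the same order at both visits?** The between-visit consistency rules cover the spirometer (section 6.8: same instrument for a given patient) and, where possible, the time of day (sections 1.4 and 6.6). None covers test order. Exclusion criterion 6 controls what happens in the hour before FeNO (food, caffeine, nicotine, strenuous exercise, certain medications). Spirometry is not on that list.

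**3. How would order enter the primary estimate?** Let *e* be the average effect of prior spirometry on measured FeNO. Let *p1* and *p2* be the shares of subjects tested spirometry-first at Visit 1 and Visit 2. On an additive scale:

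shift in mean change (Visit 2 minus Visit 1) = (*p2* − *p1*) × *e*

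- If *p1* = *p2*, the mean shift is zero, whatever *e* is.
- Since the shares differ by at most 1, the shift can never exceed *e* itself.
- The documents give no value or sign for *e*, and no value for *p1* or *p2*. The size of the shift therefore cannot be computed from them.

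**4. Is there a route by which *p1* and *p2* could differ?** Three statements can be joined. Section 3.3: "Enrollment should optimally include newly diagnosed asthma patients". Section 6.4: "Diagnosis of asthma may require spirometry measurement". Section 4.1: device "FeNO measurement will be added after taking full account of the uncontrolled asthma diagnosis and guidelines described above". If diagnosis and Visit 1 fall on the same day, spirometry could precede FeNO at Visit 1 with no matching reason at Visit 2, so *p1* > *p2*. If prior spirometry lowered FeNO, baseline would be too low and the fall understated. If it raised FeNO, the fall would be overstated. This route is an inference: no section says that diagnostic spirometry is done on the day of Visit 1, or how often.

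**The case against.** The strongest case on the other side has four parts.

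- **Preference plus permission.** Section 6.6 is headed as guidance, a should followed by a may is ordinary drafting, and every descriptive section puts FeNO first. Sites will probably work in that order. This is fair as a forecast of practice. It does not make the order binding, and should is also the word used to introduce the exclusion criteria in section 4.3, so it cannot simply be read as optional.
- **External guidelines.** Section 6.6 refers to ATS/ERS guidelines, which may fix an order. Their content is not in the documents, so this cannot be judged here. An explicit permission for any sequence would still need to be reconciled with them.
- **No order effect is shown.** This stands. A reader might infer that the primary result is biased, or that order will differ between visits. The documents support neither: they give no size or direction for an order effect, no frequency of spirometry-first testing, and only an inferred route to an imbalance. Sections 3.3 and 4.2 also admit patients with a past diagnosis, for whom that route need not arise.
- **The wording change does not close that route.** This also stands. Diagnostic spirometry done earlier the same day is clinical care, and ordering the study measurements leaves it in place. Repeating spirometry after FeNO would not undo it. A reader might therefore take the reworded sentence as a complete remedy, and it is not.

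**Conclusion.** The inconsistency in section 6.6 is real and unresolved elsewhere in the documents. No section makes FeNO-first binding or asks for the same order at both visits. Because the primary endpoint is an uncontrolled within-subject change, an order mix that differs between visits could enter the estimate.

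The importance is minor. A shift requires both an effect of spirometry on FeNO and a between-visit difference in order. The documents establish neither, and with equal order shares the mean shift is zero. The sample size section expects a mean change of about 1 standard deviation, so nothing here suggests that the study's main conclusion is in danger. The conclusion rests on the text alone and on the additive relation above. It assumes no particular order effect. The reason to act is that the change is cheap and uses a rule the protocol already states.

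**What to change.** 1. **Reconcile the two sentences in section 6.6.** Limit the free sequence to the ACQ, in line with section 6.9, and apply the protocol's own FeNO-before-spirometry sentence to study measurements at both visits. For example: *Study FeNO measurements are made before study spirometry at both visits; the ACQ may be completed at any point in the visit.*
2. **Address diagnostic spirometry at Visit 1.** If the free sequence was meant to cover spirometry done for diagnosis earlier that day, say so and confine it to that case. In any event, state how such visits are handled, because item 1 does not remove them.
3. **Record test order or times at each visit**, if not already captured. Section 7.2 gives only the titles of the case report forms and section 7.3 does not describe the fields in the instrument exports, so this needs checking before a field is added.

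I would not add a formal comparison by test order. The number of affected subjects is unknown, and spirometry-first at Visit 1 would be confounded with new diagnosis, so the comparison could not isolate an order effect.

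The cost is a revised sentence in section 6.6, a short statement on diagnostic spirometry, at most one extra data field per visit, and slightly less scheduling freedom for sites.

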6.7. Guidance for Vivatmo *pro*TM Test Result Acceptance Criteria and Invalid Results

Vivatmo *pro*TM will indicate if each measurement is valid and acceptable or if it is invalid. If the first 2 exhalation measurements at a given study visit are valid then no additional measurements need be performed at that visit. A subject must produce each valid measurement within no more than 5 exhalation measurement attempts at a given study visit. If an exhalation measurement is invalid at a given study visit then exhalation measurement should be repeated at the visit with the subject performing up to a maximum of 10 exhalation measurements total (2 x 5) at the visit or until a total of 2 valid measurements are obtained. The Vivatmo *pro*TM mouthpiece should be changed after every 5 exhalation attempts

6.8. Guidance for Spirometry Testing

Electronic peak air flow spirometry testing will be performed at each study visit in accordance with ATS guidelines. Only ATS/ERS compliant electronic spirometers should be used and the same spirometer should be used on each study patient at each study visit. Participating clinical sites will use spirometers routinely used for clinical care. Spirometers will not be provided by the Sponsor to clinical sites participating in the study. Spirometry results at each study visit including fractional exhaled volume (FEV₁%), number of exhalations measured, make and model of spirometer, and spirometer reference standard used will be recorded in the designated study CRF.

6.9. Guidance for ACQ Data Collection

Subject responses to questions on the standardized Asthma Control Questionnaire (ACQ) will be obtained at any time during the study visit. This information will frequently be available prior to Vivatmo *pro*TM testing at the time of confirmation of a clinical diagnosis of asthma. ACQ responses will be recorded at each of the 2 study visits. ACQ responses will be recorded in the designated study case report form (CRF).

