8.4. Analysis of Secondary Endpoints

The relationship between changes of FeNO-values and clinical assessments (spirometry, ACQ-questionnaire) will be assessed by Spearman's rank correlation.

Repeatability will be estimated together with the 95%-confidence interval as pooled standard deviation (mean of measurement pair < 50 ppb) and CV (mean of measurement pair ≥ 50 ppb), respectively, using the residual variance component resulting from a random effects ANOVA (as used in CLSI EP05 guideline) with patient and visit as random factors. Technically, the CV is estimated as $100 \times$ standard deviation applying the random effects ANOVA on ln-transformed values. The resulting pooled repeatability is hereby estimated taking in account conditions of variability over sites and operators.

The *success rates* (proportion of patients with successful measurement within FAS) will be reported. The number of attempts necessary to obtain 2 valid replicate measurements will be tabulated in contingency tables by visit.

9. COMPLIANCE WITH GOOD CLINICAL PRACTICES (GCP), ETHICAL CONSIDERATIONS, AND ADMINISTRATIVE ISSUES

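### The symptom questionnaire may be completed after the FeNO value has been displayed, so the correlation between FeNO change and ACQ change is not protected from inflation

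*Combined protocol and SAP*

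**What the plan says.** **Timing of the ACQ.** Section 6.9: "Subject responses to questions on the standardized Asthma Control Questionnaire (ACQ) will be obtained at any time during the study visit". It adds that the answers will often be on hand before the device is used, "at the time of confirmation of a clinical diagnosis of asthma".

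**Order of assessments.** Section 6.6 says the three assessments "may be performed in any sequence at a given patient visit so long as they are all performed on the same day". The only preference stated is earlier in the same section: FeNO ahead of spirometry. No section puts the ACQ ahead of FeNO.

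**Order as listed.** The Synopsis (Study Procedures) reads: "At the first visit, after all study assessments (FeNO, Spirometry, ACQ), subjects will receive therapy by prescription of inhaled corticosteroid (ICS) medication". Section 3.5 lists FeNO, then spirometry, then ACQ and CRF questions at the first visit, and has the same steps repeated at the second. Sections 6.2 and 6.3 use this order for both visits.

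**Visibility of the reading.** Under Section 6.6 the subject exhales "guided by visual cues and auditory cues on the display of the Vivatmo" base station, and the concentration is shown on the device in ppb about 5 seconds later. The Synopsis describes the study as open label. No section hides the value from subject or staff.

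**Analysis.** Section 8.4 says the relationship between FeNO changes and the clinical assessments, including the ACQ, "will be assessed by Spearman's rank correlation". It gives no test level, target value or analysis by order of assessment.

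**The concern.** The first secondary objective (Section 2.2) compares the FeNO change with the changes in lung function and symptoms. For symptoms, a correlation is evidence that the device tracks clinical state only if the two measurements are obtained independently. The ACQ consists of the subject's own answers. If a subject has just watched a number appear and then answers questions about symptoms, the answers may lean towards the number. Part of any correlation could then come from the display and not from the disease.

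The stake is the interpretation of one secondary analysis. The primary endpoint is a device-measured change in FeNO, and neither repeatability nor success rate uses the ACQ, so none of these is touched.

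**Working it through.** **1. Can the ACQ follow the reading under the plan?** Yes. Sections 6.6 and 6.9 permit it expressly. The lists in the Synopsis and in Sections 3.5, 6.2 and 6.3 are not ordering rules, but a site that works through them takes the ACQ after the reading. The CRF numbering in Section 7.2 does not show otherwise: CRFs 4 and 6 (ACQ and spirometry) precede CRFs 5 and 7 (FeNO), yet spirometry shares the ACQ form and is the assessment that Section 6.6 prefers after FeNO.

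**2. Would the same order at both visits cancel the effect?** No. Suppose the reported ACQ at visit v is S_v + c·F_v, where S_v is the uninfluenced score, F_v the displayed FeNO value and c the influence of seeing it. Then

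ΔACQ = (S₂ − S₁) + c·(F₂ − F₁) = ΔS + c·ΔF.

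The reported change carries a term in ΔF, the quantity it is then correlated with. If only Visit 2 is exposed, the extra term is c·F₂.

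**3. What kind of influence matters?** Only one that tracks the individual reading. In simulation (n = 120, 2,000 runs), a uniform shift of 0.5 SD in every subject's ACQ change, unrelated to FeNO, gives a mean Spearman coefficient of 0.00.

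**4. Illustration of size.** The plan has no figure for this correlation to reproduce. Its sample-size statement concerns only the primary endpoint. At effect size 1 with a paired t-test at an assumed two-sided 5%, N = 10 gives power 0.803 and N = 13 gives 0.911, so the stated 10 and 13 are confirmed; they have no bearing here.

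Inputs: n = 120 (Synopsis, Sample Size), taken as complete pairs. Assumed, not in the documents: standard normal changes, true correlation 0, a fraction f of subjects exposed, and a shift of b SD of ACQ change per SD of FeNO change. Changes are oriented so that a positive coefficient means FeNO and symptoms move together. Model: x ~ N(0,1), e ~ N(0,1), y = e + g·b·x, with g = 1 for exposed subjects and 0 otherwise.

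| b | mean Spearman, all exposed | mean Spearman, half exposed |
|---|---|---|
| 0 | 0.00 | 0.00 |
| 0.1 | 0.09 | 0.05 |
| 0.2 | 0.19 | 0.10 |
| 0.3 | 0.27 | 0.14 |
| 0.5 | 0.43 | 0.22 |

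Closed-form check at b = 0.2. The Pearson correlation is f·b/√(1 + f·b²), and under normality Spearman = (6/π)·arcsin(r/2).
- All exposed: r = 0.2/√1.04 = 0.196, Spearman = 0.19.
- Half exposed: r = 0.1/√1.02 = 0.099, Spearman = 0.095 (the second is approximate, since a mixture is not exactly normal).

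Both agree with the simulation. With the ACQ always first, b = 0 by design and the mean is 0.00.

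**The case against.** **The reaction is assumed.** Section 6.6 says the value is displayed; nothing says the subject is told it or helped to interpret it. Subjects may be as young as 7. To respond to a fall, a subject would have to remember a ppb figure from at least 14 days before (Section 6.3). This largely stands: the mechanism is plausible, not documented. Recall is not strictly needed, because step 2 shows that reacting to each visit's number as high or low is enough. The subject must still give the number some meaning.

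**The simulation returns its own input.** With b added directly, b is in effect the correlation. This stands. The table shows what a given influence would do, not how large the influence is. Full exposure is also an upper case, since Section 6.9 expects many ACQs to come first.

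**No significance test is planned.** A reader might want to call the simulated share of runs with p < 0.05 (52% at b = 0.2 with all exposed, 17% with half) an inflated false-positive rate. Section 8.4 sets no level or success criterion, so the plan has no such error rate to inflate.

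**Differential exposure between visits.** A reader might infer from Section 6.9 that the ACQ is uninformed at Visit 1 and informed at Visit 2, and hence that the mean ACQ change is biased. The reason given there, confirmation of diagnosis, does belong to Visit 1. But Section 3.5 has the same steps repeated at the second visit, which suggests the same order at both. The difference is an inference, and a bias in mean ACQ change is not established.

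**Operator knowledge.** The Synopsis has one operator guide the FeNO measurements, but no section says that person administers the ACQ. No claim is made on that ground.

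None of this removes the core: the order is expressly free, the reading is unmasked, and the two changes are then correlated.

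**Conclusion.** The concern holds in limited form. The plan permits, and its own lists suggest, collecting the ACQ after the FeNO value has been displayed, so the Spearman correlation between the two changes is not protected from inflation. That much rests on the text, plus the reasonable inference that a subject following the display can see the result.

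The size is unknown. Under the stated assumptions, a shift of 0.2 SD per SD would turn a true correlation of 0 into about 0.19 with all subjects exposed and about 0.10 with half. These figures are illustrative. The documents do not support saying that the correlation will be produced by knowledge of the result, that exposure differs between visits, or that a 5% error rate is breached.

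This is an inexpensive improvement to a secondary analysis. It should be made before enrolment, because the CRF titles in Section 7.2 show no item for the order of ACQ and FeNO. If the order is not recorded at the visit, its influence may not be examinable afterwards.

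**What to change.** 1. In Section 6.9, replace the free timing with a requirement that the ACQ be completed before the first FeNO exhalation at both visits.
2. In Section 6.6, exempt the ACQ from the sentence allowing any sequence. The preference for FeNO ahead of spirometry can stay as it is.
3. Bring the lists in the Synopsis and Sections 3.5, 6.2 and 6.3 into the same order, so that they do not point sites the other way.
4. On CRFs 4 and 6, record whether the ACQ preceded the FeNO measurement, if the forms do not already capture this. The templates are not in the documents, so it cannot be checked here.
5. In Section 8.4, add a sensitivity analysis that repeats the FeNO–ACQ correlation without subjects whose ACQ followed a reading at either visit.

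The cost is a small loss of scheduling flexibility and one extra CRF item per visit. No visit or procedure is added, and Section 6.9 already expects the ACQ to be available first in many cases.
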